6.4.3.1 Primary VE Analysis

For the primary analysis, Cox proportional hazards regression will be used to estimate vaccine efficacy against SARS-CoV-2 infection among baseline SARS-CoV-2 seronegative participants, as measured by one minus the hazard ratio (HR) in the Immediate Vaccination vs. Standard of Care arms. This analysis that restricts attention to randomized participants will be supported by a co-primary analysis that combines data from the Standard of Care arm with data from the Vaccine Declined Group. An additional supportive analysis will restrict to the D29- set, counting only infection events diagnosed post-Day 29. These analyses supporting the primary objectives of the study will be detailed in the SAP. To improve precision when comparing randomized groups, and to avoid bias when including non-randomized participants, primary analyses will adjust for an SAP-specified set of “risk” variables, or a composite risk score based on them, that are potentially associated with SARS-CoV-2 exposure including demographics and behaviors captured using the risk assessment tool. Inference will be based on a 2-sided score-based CI and 2-sided score-test for $H_0: VE = 0\%$ with a type 1 error rate of 0.05, although primary interest is in estimation as opposed to hypothesis testing and the study is designed to ensure that the lower limit for the CI will lie above 30% with high probability under $VE > 60\%$. The baseline hazard function in the Cox model will be stratified by study site and randomization stratum, which improves precision of the VE estimate and accounts for the fact that SARS-CoV-2 infection incidence may vary widely across study sites. Description of the risk variables under consideration and of the derivation of a risk score based on them will be described in the study SAP.

The potential impacts of the open-label and observational aspects of the study design will be factored into the choice of efficacy analysis. If there is evidence of differential retention of study participants across groups, or differential adherence to study procedures affecting ascertainment of endpoints such as collection of daily swabs, the analyses will adjust for the differential censoring distribution across groups- as well as potentially informative censoring- as described in the study SAP. At a minimum, these analyses will be performed as sensitivity analyses, complementing the primary analyses described above.

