2.5 Sample Size and Power

At the design stage, sample size calculations assumed 48,000 person-months of follow-up (even between vaccinated and unvaccinated, with the latter potentially including the Vaccine Declined group), 5% loss-to-follow-up rate, 10% baseline sero-positivity, 98% per-protocol rate, SARS-CoV-2 infection endpoint post Day 29 among baseline seronegative participants in the D29- set with 4% event incidence over 16 weeks (constant over time) among unvaccinated. Under these assumptions, the study had 90% power to detect $VE > 57\%$ using one-sided 0.025-level log-rank test. Additionally, assuming 50% VE we expected (50% probability) at least 225 post-Day 29 events to be available to estimate the vaccine effect on mean peak log10 viral load. The assumed 225 events, SD in peak log10 viral load = 1.8 (equal in both arms), 1-sided 0.025-level two-sample t-test yielded 96.9% power.

Due to early termination of the trial, the study is underpowered to address primary study objectives.

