Baseline SARS-CoV-2 negative set (Main study primary data set): To account for ramping vaccine efficacy (VE), the protocol stipulated that primary analyses would be conducted among all baseline SARS-CoV-2 negative participants, and again among participants in the “Day 29 Negative Set”—the set of participants without seroconversion or PCR-confirmed infection on or prior to second vaccination on Day 29. The intent of this plan was to evaluate effects of the full two-dose vaccine regimen. Given that time of second vaccination is not easily defined in the SoC and Vaccine Declined groups and given that some participants in the Immediate Vaccination group began swabbing and accruing person-time and infection events before first vaccination, primary analyses will instead be conducted among all eligible enrolled baseline SARS-CoV-2 negative participants (Baseline SARS-CoV-2 negative set). All person-time and events will be included, and ramping VE will be accommodated using analyses that estimate vaccine effects according to number of doses received. Baseline SARS-CoV-2 negativity will be defined as PCR negative based on the first resulted (see section 3.2.9 for exclusions) nasal swab and seronegative based on the first qualifying (see section 3.2.8 for exclusions) blood sample closest to the first resulted swab. Note that blood collection for determining baseline serostatus was intended to occur coincident with initiation of swabbing; however, some participants had blood collected well before they began swabbing, and others had blood collected well after the initiation of swabbing. The analysis will summarize the distribution of time between first resulted swab and first blood. Qualifying blood sample closest to the first resulted swab date will be defined as either the closest qualifying blood sample on or before the first resulted swab date (if it exists) or the closest qualifying blood sample after the first resulted swab date (if no qualifying blood sample exists on or before the first resulted swab date). Primary analyses of vaccine efficacy against infection (VES) and of the vaccine effect on viral load (ΔVL) will be conducted among Baseline SARS-CoV-2 negative set participants that were enrolled as randomized.

All primary and secondary analyses will be done according to enrollment group, ie, Immediate Vaccination Group, Standard of Care Group, or Vaccine Declined Group.

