7.1 Descriptive analysis

Tables

The following table will be used to describe SARS-CoV-2 incidence by group and vaccine receipt. It will be produced first including only baseline SARS-CoV-2 negative participants, and then again including all FAS-P participants. Each participant's incident exposure period will start from either the first nasal swab (if the first swab result was negative) or 90 days after the first swab (if first swab positive). The participant's exposure will be broken down to unvaccinated, one-dose and two-dose exposure periods. The unvaccinated exposure period will include days and events up to (and including) the date of the first study vaccination or censoring, whichever occurs first. The one-dose exposure period will include days and events starting the day after the first vaccine and ending on the date of the second vaccine or censoring, whichever occurs first. The two-dose exposure period will include days starting the day after the second vaccine. The 95% confidence interval for the incidence rate will be calculated using the exact method.

Group	Exposure: number of study vaccine doses	Censoring	Number of incident infections	Person- years	Incidence rate (95% CI)
Immediate arm	Unvaccinated	Outside vaccination		See note 1	
	Unvaccinated	ITT		See note 1	
	Single dose	Outside vaccination		See note 2	
	Single dose	ITT		See note 2	
	Two doses	Outside vaccination		See note 3	
	Two doses	ITT		See note 3	
SoC arm	Unvaccinated	Outside vaccination		See note 4	
	Unvaccinated	ITT		See note 4	
Vaccine Declined arm	Unvaccinated	Outside vaccination		See note 4	
	Unvaccinated	ITT		See note 4	

Note 1: Total number of person-years from the incident follow-up start to the first of study vaccination, infection or censoring.

Note 2: Total number of person-years from the last of incident follow-up start and first dose to the first of second dose, infection or censoring.

Note 3: Total number of person-years from the last of incident follow-up start and second dose to the first of infection or censoring.

Note 4: Total number of person-years from the incident follow-up start to the first of infection or censoring.

Incident follow-up start = either the first nasal swab (if the first swab result was negative) or 90 days after the first swab (if first swab positive)

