7.2 Primary efficacy analysis

Objective: To evaluate the effect of mRNA-1273 vaccination on acquisition of SARS-CoV-2 infection

Endpoint: Incident infection by study PCR subject to Outside Vaccination Censoring.

Data sets: Baseline SARS-CoV-2 negative participants enrolled as randomized

Exposure: Randomization, and number of study vaccine doses received within the Immediate Vaccination group

Adjustment covariates: Baseline factors: Age, sex, race/ethnicity, place of residence, attributes from the Baseline SARS-CoV-2 Infection Risk Assessment CRF

Analysis: Vaccine efficacy will be estimated using a time-varying Cox model that stipulates the following hazard function

$$h(t) = h_{0S}(t) \exp \{ \alpha_1 I(T_1 < t) + \alpha_2 I(T_2 < t) + \beta X \}$$

where t is time since study initiation (calendar time), T_1 is the calendar time of the first dose of study vaccine and T_2 is the calendar time of the second dose of study vaccine, $h_{0S}(t)$ is an unspecified baseline hazard that depends on study site, and X is a vector of baseline covariates identified in Section 3.2.5 and 3.2.6 as associated with exposure and/or censoring. The efficacy of one dose of study vaccine will be measured by $1 - e^{\alpha_1}$ and the efficacy of two doses measured by $1 - e^{\alpha_2}$. The model will be fit using the R survival package. Two-sided 95% confidence intervals for the VE estimates will be calculated using the Wald method.

If the set of covariates that is associated with SARS-CoV-2 exposure and/or censoring is too large to permit covariate adjustment, an IPCW analysis will be performed. Specifically, the above Cox model will be fit using a time-dependent weight that corresponds to a (standardized) probability of censoring. The analysis will be implemented using the R ipcswitch package.

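### SAP 7.2 replaces the protocol's score-based interval with a Wald interval for dose-specific VE, without explanation; a dose period with no infections would then have no finite lower VE limit.

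*SAP*

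**What the plan says.** Protocol 6.4.3.1 plans a Cox model with one Immediate Vaccination versus Standard of Care hazard ratio and states: "Inference will be based on a 2-sided score-based CI and 2-sided score-test", two-sided, "with a type 1 error rate of 0.05".

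SAP 7.2 keeps a Cox model but gives it two time-varying indicators, one switched on at the first study dose (coefficient α1) and one at the second (coefficient α2). It then says "The efficacy of one dose of study vaccine will be measured by" 1 − exp(α1), and gives 1 − exp(α2) as the two-dose measure. On intervals it says: "Two-sided 95% confidence intervals for the VE estimates will be calculated using the Wald method". It names no score, profile-likelihood, exact or penalised alternative. Its one fallback, inverse-probability-of-censoring weighting (IPCW), is triggered by too many covariates, not by too few events.

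SAP 3.1 explains the split by dose as the replacement for the Day 29 Negative Set analysis, in these words: "All person-time and events will be included, and ramping VE will be accommodated using analyses that estimate vaccine effects according to number of doses received". SAP 2.5 adds: "Due to early termination of the trial, the study is underpowered to address primary study objectives". For the descriptive tables SAP 7.1 says "The 95% confidence interval for the incidence rate will be calculated using the exact method", but that covers incidence rates, not VE. SAP 9.2 (COVID-19 disease) does not mention Wald; it takes over the method by calling its VE estimation analogous to that for the acquisition endpoint.

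**The concern.** The SAP flags its departures from the protocol on the analysis set (3.1) and the disease definition (9.2), but not on the interval method for the primary VE estimate. The new method is weakest in the setting the SAP creates. Early stopping reduces the number of events, and dividing vaccinated time into one-dose and two-dose periods reduces the number in each period further. A Wald interval is the estimate plus or minus a multiple of its standard error, and neither is finite when a period has no events. That outcome becomes more likely the better the vaccine works. The trial could then print no usable limit for two-dose VE although the data rule out low efficacy.

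**Working it through.** **1. Design size.** Inputs from protocol Table 6-2 and section 6.1: 6000 per group, 10% seropositive, 98% per-protocol, 4% infection and 5% loss over 16 weeks, VE 50% from week 2, events counted from week 4 to week 16.
- At risk per group: 6000 × 0.90 × 0.98 = 5292.
- Expected events: 153.0 unvaccinated + 77.3 vaccinated = 230.3, against the protocol's 225 (150 + 75). The figure is reproduced closely.
- Wald at 75 versus 150: SE = √(1/75 + 1/150) = 0.1414; hazard ratio 0.5 × exp(±1.96 × 0.1414); VE 34.0% to 62.1%.
- Score (Wilson interval for 75 of 225, converted to a rate ratio): 34.1% to 62.1%.

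At the planned size the choice of method makes no difference.

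**2. No events in the two-dose period.** Assume equal person-time, 0 two-dose infections and m Standard of Care infections. Conditional on the total, the upper rate-ratio limits are:
- Score: z²/m, with z² = 3.84.
- Likelihood ratio: exp(z²/2m) − 1.
- Wald: none, because log(0) and 1/0 are not finite.

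For m = 20 the score limit is 3.84/20 = 0.192, so the lower VE limit is 80.8%. The likelihood-ratio limit is exp(0.0960) − 1 = 0.101, so the lower VE limit is 89.9%. For m = 5, 10 and 40 the score lower limits are 23.2%, 61.6% and 90.4%. If the vaccinated period has only a quarter of the control exposure (4 of 16 weeks), the score lower limit at m = 20 falls to 1 − 4 × 0.192 = 23.2%.

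**3. The SAP's own model, fitted to simulated data with 600 per arm.**
- 28 control, 4 one-dose and 0 two-dose infections: α2 is −10.2 (SE 34) after 10 Newton steps and −20.2 (SE 5070) after 20. The fit does not converge. The profile-likelihood lower limit for two doses versus control is 89.5%.
- 25 control, 0 one-dose and 9 two-dose infections: α1 goes to minus infinity. The first-dose indicator stays on after dose 2, so α2 goes to plus infinity to compensate, and both reported intervals fail. The sum α1 + α2 remains estimable, with Wald VE interval −11.9% to 76.7%.

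**4. Which parameter the 81% belongs to.** It is for two doses versus unvaccinated, which is α1 + α2 under the coding in 7.2. α2 alone is the increment over one dose. With 0 two-dose infections, 12 weeks of two-dose exposure and 4 weeks of one-dose exposure, the score lower limit for 1 − exp(α2) is 1 − (3.84/k)(4/12), where k is the number of one-dose infections. This gives −28%, 36% and 68% for k = 1, 2 and 4. With k = 0, α2 is not identifiable by any method.

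**5. Chance of an empty period.** The documents give no realised enrolment or event counts, so the arm size N is assumed. Weekly hazard = −ln(0.96)/16 = 0.00255; 90% seronegative; no loss. The expected count is N × 0.90 × 0.00255 × weeks × (1 − VE), and the chance of none is exp(−expected count). Example: N = 250, 4 weeks, VE 50% gives an expected count of 1.15 and a chance of 32%.

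| N per arm | One-dose (4 wk), VE 50% / 90% | Two-dose (12 wk), VE 50% / 90% |
|---|---|---|
| 250 | 32% / 80% | 3% / 50% |
| 500 | 10% / 63% | 0.1% / 25% |
| 1000 | 1% / 40% | 0% / 6% |
| 6000 | 0% / 0.4% | 0% / 0% |

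**6. Coverage when every period has events.** In Poisson simulation with 1 versus 15, 2 versus 15 and 3 versus 20 expected events, Wald coverage among runs with a finite interval is 94%, 96% and 97%; score coverage is about 96% overall.

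**The case against.** The strongest reply is that the failure is hypothetical. The documents report no counts, an empty two-dose period is unlikely at VE 50%, and the SAP was written after early stopping and unblinding, so its authors may have known that no period was empty. SAP 2.4 also treats the randomized analyses as post-hoc, SAP 2 says in general terms that some methods had to change, and 7.1 gives exact intervals for incidence by number of doses. Most of this stands as a limit on size. It does not supply a reason for the switch or a rule for an empty period, and an incidence interval is not a VE interval.

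A reader might infer several stronger things that the documents do not support:
- **That a dose period was in fact empty, or that Wald was chosen with knowledge of the data.** Nothing in either document shows this.
- **That Wald undercovers badly.** Coverage falls to 60%, 83% and 92% in the three scenarios of step 6 only if unbounded intervals are scored as misses. Those intervals are uninformative, but they do not exclude the true value.
- **That about 81% would be the limit for the SAP's two-dose measure as coded.** It would not (step 4).
- **That the split by dose is itself unexplained.** SAP 3.1 explains it.
- **That the protocol's method can simply be put back.** It was specified for a single hazard ratio, so it has to be applied to each dose contrast, and an ordinary profile interval is not valid for the weighted IPCW fit.

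**Conclusion.** The point holds as a conditional weakness. The change from score to Wald for the primary VE interval is real and unexplained. Wald gives no finite lower limit when a dose period is empty, and under the cumulative coding an empty one-dose period destroys both reported intervals. What is lost can be substantial: a lower limit of about 81% (score) or 90% (likelihood ratio) with 0 against 20 infections at equal person-time. The probabilities in step 5 rest on assumed arm sizes of 250 to 1000, 4% incidence over 16 weeks, 10% seropositivity and no loss. If every period has events, Wald coverage is acceptable; with ample events the methods nearly agree. The change is worth making but does not undermine the analysis as a whole.

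**What to change.** In SAP 7.2, replace the Wald interval with score-based or profile-likelihood 95% intervals for two contrasts: one dose versus unvaccinated, and two doses versus unvaccinated. The second is α1 + α2 under the current coding; alternatively, recode the one-dose and two-dose periods as mutually exclusive so that each coefficient is its own contrast with unvaccinated time. Add a rule that, when a dose period has no infections, the finite lower VE limit is reported with the upper limit at 100%. Section 9.2 needs no separate edit, because it inherits the method. If Wald is kept, give the reason for leaving the protocol's method and say what will be reported for an empty period.

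The cost is small: a few sentences and slightly more code. The interval may still be wide when control events are few. If the IPCW analysis is used, it needs a robust score or bootstrap interval.

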7.2.1 Supportive analyses

- **ITT analysis:** We will repeat the primary analysis using ITT censoring.
- **All FAS analysis:** includes those baseline SARS-CoV-2 negative and baseline SARS-CoV-2 positive in the analysis.

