6.3 Randomization

A participant's randomization assignment will be computer generated and provided to the CRS study staff through a Web-based randomization system.

Randomization will be stratified. The randomization will be done in blocks to ensure balance among contemporaneously evaluated Immediate Vaccination and Standard of Care arms within levels defined by study site and type of residence.

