6.4 Statistical analyses

This section describes the final study analyses which will occur after the last main study participant has completed the Month 4 visit. All data from enrolled participants will be analyzed according to the initial group assignment regardless of how and when in-study and outside-study vaccinations are received. Follow-up and endpoints that accrue post-outside-study-vaccination will be censored for primary and secondary analyses. In the rare instance that a participant receives study vaccination at the wrong time, the Statistical Analysis Plan (SAP) will address how to analyze the data. Analyses are modified intent-to-treat in that individuals who are randomized but not enrolled do not contribute data and hence are excluded. Because of the brief length of time between randomization and enrollment, few such individuals are expected.

The SAP will specify how data from the Vaccine Declined group will contribute to assessing primary and secondary objectives. Wherever possible, analyses will limit to data collected on randomized participants, and will entail comparing outcomes between those randomized to Immediate Vaccination or Standard of Care. However, if operational data on enrollment, retention, adherence to study procedures suggest that there will be insufficient unvaccinated follow-up for the Standard of Care Group to permit a specific analysis, data from the Standard of Care Group will be combined with data from the Vaccine Declined Group, with methods fully pre-specified in the SAP.

Analyses for primary endpoints will be performed using SAS and R. All other descriptive and inferential statistical analyses will be performed using SAS, StatXact, or R statistical software.

In general, no formal multiple comparison adjustments will be employed for multiple secondary endpoints. However, multiplicity adjustments will be made for

certain immunogenicity assays, as discussed below, when the assay endpoint is viewed as a collection of hypotheses (eg, testing multiple peptide pools to determine a positive response).

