2.3 Randomization

14,400 participant slots (20% more than the planned 12,000 participants) were randomized into the Immediate and SoC groups with the 1:1 allocation ratio, stratification by site and place of residence (Dormitory or campus housing, Fraternity or sorority house, Apartment building or condo, Stand-alone house (non-fraternity or sorority, Shelter, RV / Trailer, Staying with friends / Couch surfing, No residence and Other) and 1:1:1 mix of block sizes 8, 10 and 12 created in a random order. Released randomized participants could not be re-randomized into the study (but were allowed to enroll in the Vaccine Declined group). The released randomization slots were not re-used by other (replacement) participants.

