7.2.2 Exploratory analyses

The time-varying Cox model of 7.1.1 will be used for estimation, but ITT censoring will be employed.

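### The 'ITT analysis' in SAP 7.2.1 is the study-dose model with different censoring, and no SAP model estimates the protocol's Immediate vs Standard of Care hazard ratio stratified by site and randomisation stratum

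*SAP*

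**What the plan says.** **Protocol.** Section 6.4.3.1 measures vaccine efficacy (VE) against infection "as measured by one minus the hazard ratio (HR) in the Immediate Vaccination vs. Standard of Care arms". It adds that "The baseline hazard function in the Cox model will be stratified by study site and randomization stratum", and asks for a score-based confidence interval. Section 6.3 randomises in blocks "within levels defined by study site and type of residence". Section 6.4 says that data "will be analyzed according to the initial group assignment regardless of how and when in-study and outside-study vaccinations are received", and its next sentence censors follow-up after outside vaccination for primary and secondary analyses. Section 6.4.3 repeats that censoring rule. Section 6.4.3.2 adds a secondary time-varying analysis that counts follow-up after outside Moderna vaccination.

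**SAP.** Section 7.2 lists randomisation first on its exposure line, but the hazard it writes down is h0S(t)·exp{α1·I(T1<t) + α2·I(T2<t) + βX}. T1 and T2 are the times of the first and second study dose, S is study site, and intervals are Wald. X holds the covariates found in 3.2.5 and 3.2.6. The ITT analysis in 7.2.1 reads: "We will repeat the primary analysis using ITT censoring". Section 7.2.2 reads: "The time-varying Cox model of 7.1.1 will be used for estimation, but ITT censoring will be employed". The SAP has no section 7.1.1.

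**The concern.** A reader who sees a supportive analysis labelled ITT, in a trial with two randomised arms, will take it as the comparison that randomisation protects. The open-label design and access to vaccine outside the study make that comparison the natural check on a dose-received model. Here the label describes only the censoring rule. The dose contrasts compare person-time classified by what participants received after randomisation, and the supportive analysis keeps that classification. If the report carries only these models, the protocol's primary estimand is never estimated and nothing tells the reader so.

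**Working it through.** **1. The plan's own figure.** Protocol 6.1 and SAP 2.5 state 90% power at VE above 57%, with 4% incidence over 16 weeks, from a one-sided 0.025-level log-rank test; protocol 6.1 gives the null as VE ≤ 30%.

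- Inputs (protocol Table 6-2 and 6.1): 6,000 per group, 10% seropositive, 98% per protocol, 5% loss over 16 weeks, VE from day 14, events counted over weeks 4 to 16.
- N per group = 6,000 × 0.90 × 0.98 = 5,292. Constant hazards give 153.0 unvaccinated and 66.5 vaccinated events.
- Power = Φ{ln(0.70/0.43)/√(1/153.0 + 1/66.5) − 1.96} = Φ(0.487/0.147 − 1.96) = 91.3%.

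The stated figure reproduces within two points. It belongs to a comparison of two groups with one coefficient, and the SAP model has no such coefficient.

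**2. Where each block of person-time goes.**

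| Person-time | Protocol 6.4.3.1 | SAP 7.2 (outside-vaccination censoring) | SAP 7.2.1 (ITT censoring) |
|---|---|---|---|
| Immediate, before dose 1 or never dosed on study | Immediate | reference | reference |
| Immediate, after dose 1 | Immediate | e^α1 | e^α1 |
| Immediate, after dose 2 | Immediate | e^(α1+α2) | e^(α1+α2) |
| SoC, no vaccine | SoC | reference | reference |
| SoC, after outside vaccine | censored | censored | reference |

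Under ITT censoring the model follows doses received in one arm and assignment in the other. SAP 3.1 confirms that the first row is not empty: some Immediate participants accrued time and infections before their first dose.

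**3. Neither coefficient is an arm contrast.** I(T1<t) stays at 1 after dose 2, so e^α2 compares dose 2 with dose 1. If VE were 50% after each dose, 1−e^α1 would be 50% and 1−e^α2 would be 0%. The arm-level VE is 1 − {q + (1−q)[g + 4(1−VE1) + (12−g)(1−VE2)]/16}, where g is weeks from start of follow-up to dose 1 and q is the share never dosed. Assuming g from 0 to 3 and q from 0 to 10%, it runs from 50.0% (g=0, q=0) to 36.6% (g=3, q=0.1: 0.1 + 0.9 × 9.5/16 = 0.634). This shows that the three quantities differ. It is not an estimate for this trial.

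**4. Search for an arm model elsewhere in the SAP.** The Cox models in 3.2.5 and 3.2.6 are fitted within the SoC group, or separately within Vaccine Declined. The inverse-probability-of-censoring option in 7.2 refits the same hazard. Disease VE in 9.2 is analogous to 7.2. What remains by arm is the rate table split by dose, the monthly incidence plots and the Kaplan-Meier curves in 7.1, all descriptive.

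**5. Residence.** It is a randomisation stratum (protocol 6.3, SAP 2.3) but not a stratum in SAP 7.2. It appears in that section's list of adjustment covariates, while the definition of X admits only variables selected in 3.2.5 and 3.2.6. Those sections screen in opposite directions as worded: 3.2.5 keeps p-values above 0.10 and 3.2.6 keeps those below. Whether residence enters is therefore unclear.

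**The case against.** The strongest reply is that the SAP explains its choice. Section 3.1 says that dose terms accommodate ramping efficacy and pre-dose swabbing, and sections 2.4 and 2.5 call the randomised analyses post hoc and underpowered. The rate table gives events and person-years by arm and dose under both censoring rules, so crude by-arm rates can be summed. All of this stands. It supports keeping the dose model and lowers the risk of misreading. It does not make a dose model an ITT analysis, and a crude summed rate is not a hazard ratio stratified by site and residence.

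Four stronger readings are tempting.

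- *The label inflates VE by many points.* Assume VE 80% after either dose and 40% outside uptake spread evenly, so the SoC hazard is 1 − 0.2 × 0.8 = 0.84. With 10% of Immediate time undosed, by-arm VE is 1 − 0.28/0.84 = 66.7% and 1−e^α1 is 1 − 0.2/(0.94/1.1) = 76.6%. With 2% undosed (a loose reading of the 98% per-protocol planning rate) they are 1 − 0.216/0.84 = 74.3% and 1 − 0.2/(0.86/1.02) = 76.3%. The result turns on a share that the documents do not give, and the gap is largely a difference of estimand.
- *An ITT-censored arm model recovers the protocol's hazard ratio.* It does not, because the protocol censors at outside vaccination.
- *Switchers are wrongly dropped.* SAP 2.3 says released randomised participants "could not be re-randomized into the study (but were allowed to enroll in the Vaccine Declined group"). Protocol section 6 analyses by enrolment group, so leaving them out of the randomised comparison follows the protocol. No reason for switching is given.
- *Wald limits will fail because the two-dose group will have no events.* Nothing in the documents shows this. The case for a score-based interval is that the protocol specified one.

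**Conclusion.** The point holds as a matter of what the models contain. The SAP's ITT analysis is not by randomised arm, and the protocol's stratified Immediate vs SoC hazard ratio is left without a model. This rests on the written hazard in SAP 7.2. The SAP's own references to randomisation (7.2) and enrolment group (3.1) are not carried into it. No numerical bias is claimed. Two smaller points follow: 7.2.2 cites a missing section and, as worded, adds nothing clear to 7.2.1; and the protocol 6.4.3.2 analysis counting outside Moderna doses appears nowhere in the SAP. A reader might infer that 7.2.2 was meant to replace that analysis, but the faulty reference does not show it.

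**What to change.** 1. In 7.2.1, add a Cox model with a fixed randomised-arm indicator among participants enrolled as randomised. Stratify the baseline hazard by site and by the four-level residence grouping in SAP 3.2.5; if strata are too sparse, stratify by site and adjust for residence. Use the protocol's score-based interval.
2. Run it under outside-vaccination censoring, which is the protocol's estimand, and under ITT censoring.
3. Rename the present analysis 'study-dose model with ITT censoring'.
4. Correct the reference in 7.2.2. Either specify there the protocol 6.4.3.2 analysis that counts outside Moderna doses, or state that it is dropped.
5. State that residence is always included in 7.2.

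The arm models use data already collected. The cost is a few extra Cox fits, some SAP wording, and an arm-level interval that may be wide with few events.
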